#### • Discharge data:

Inpatient morphine equivalents (24 hours prior to discharge), average pain score (24 hours prior to discharge), discharge pain medications prescribed, discharge morphine equivalents prescribed, hospital length of stay and discharge disposition.

- Actigraphy based sleep and activity data (e.g. average hours of sleep, average daily steps): Study participants will be provided with a wrist actigraphy device to wear during their hospitalization and throughout their recovery until their 2-week follow up appointment with the surgical team. Participants will return their actigraphy devices at the 2-week follow up appointment or be provided a pre-paid envelope to take home and mail back the device after the visit. Wrist actigraphy is a valid and objective tool to measure activity patterns and sleep-related parameters, which has been used in patient populations with both acute and chronic pain. Actigraphy data includes objective quantitative measures of sleep, such as total sleep time, sleep latency, fragmentation, wake after sleep onset, and sleep efficiency. Additionally, activity level is also captured using wrist actigraphy, including total activity time, steps, physical activity intensity, and total energy expenditure. Participants will receive, and be trained on how to wear, a screen-less actigraphy device on their wrist (GT3XP-BTLE, Actigraph, LLC, USA). Devices will be set to record in 30-second epochs at a medium sensitivity level for scoring sleep and wake time. Wear time validation will be accomplished using the Choi algorithm, as it more accurately estimates time worn accounting for forward and backward motions. The sleep data will be computed using the Cole-Kripke algorithm, which accurately distinguishes sleep from wakefulness approximately 88% of the time. Metabolic equivalent of tasks and energy expenditure will be measured with the Freedson algorithms. By uniquely pairing actigraphy data with PROMIS patient-reported pain, sleep, and physical function measures, this study will be one of the first to provide a robust analysis of sleep quality and activity in tandem to pain presentations in adult surgical patient populations during hospitalization and throughout immediate post-discharge recovery following surgery. These research efforts adhere to recommended best practices for using actigraphy to examine health outcomes.35

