#### VISIT SCHEDULE AND ASSESSMENTS

Assessment	Visit 1:	Visit 2:	Visit 3:	Visit 4:
	Inpatient	2 Weeks (±	6 Weeks (±	3 Months (±
	Hospitalization	7 days)	14 days)	14 days)
Demographics	X			
Trauma registry data	X			
Comprehensive Social Determinants of Health (SDOH) Survey	X			
Revised Opioid Risk Tool (ORT)	X			
Short Form 36 Health Survey Questionnaire (SF-36)	X			X
Pain Management Questionnaire (PMQ)	X	X	X	X
Prescription Drug Use Questionnaire (PDUQ)	X	X	X	X
PTSD Screener	X			X
PROMIS: Sleep Disturbance	X	X	X	X
PROMIS: Physical Function	X	X	X	X
PROMIS: Pain Interference	X	X	X	X
PROMIS: Prescription Pain				X
Medication Misuse				
Opioid Literacy Tool (OLT)	X			X
Patient Satisfaction Survey		X		
Naloxone Questionnaire		X	X	X
PAC-SYM	X	X	X	
Inpatient Opioid Utilization (MME/day)	X			
Inpatient Numerical Rating Scale (NRS) Pain Score	X	X	X	X
Medication Electronic Monitoring (MEMS) devices:		X	X	X
Defense and Veterans Pain Rating Scale (DVPRS)	X	X	X	X

Inpatient Sleep Actigraphy	X				l
Field notes and participant quotes	X	X	X	X	l
Participant Compensation	X	X		X	ı

Questionnaires/surveys and meetings with the Life Care Specialist will occur during scheduled telehealth appointments. No charges will be generated specifically relating to the research components.

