Aim 2: Evaluate the effectiveness of Life Care Specialist intervention on reducing long-term postoperative opioid medication utilization. As described above, a systematic machine learning guided model construction approach will be used to also test the working hypothesis that participants in the intervention will report decreased utilization of opioid pain medications both in the inpatient and outpatient setting up to 3-months postoperatively. Separate mixed-effects models will be constructed to estimate differences in average MME/day during inpatient hospitalization as well as to estimate difference in average MME/day over every study follow up point up to 3-months postoperatively.

Aim 3: Explore the feasibility of utilizing actigraphy devices to capture postoperative functional outcomes among patients during their hospitalization and up to 2-weeks postoperatively following orthopaedic trauma. Generalized estimating equations (GEE) will be used to explore changes in functional outcomes over the 2-

week postoperative period. For example, activity will be measured as average step per day and sleep will be measured as average nightly sleep efficiency and duration. Separate GEE will be computed for each actigraphy related measure. In the event a significant change in any of the objective outcomes, a linear mixed-effect model will be constructed to ascertain any significant differences in actigraphy collected outcomes exist between participants in the intervention and the control arms over the two-week postoperative period.

Power: A sample of 200 provides 85% power ( $\alpha$ =0.05) to detect a difference as small as 0.5 in the mean pain score between the intervention arm and the controls using repeated measures mixed effects modeling (Power Analysis and Sample Size Software, NCSS, Kaysville, UT, USA). All analyses will be conducted in R (R Core Team, Vienna, Austria) by the Co-PI and his team at the Nell Hodgson Woodruff School of Nursing ([name]). The *glmnet* package will be used to determine which variables should be included in the regression models using a LASSO approach, the *lme4* package will be employed to compute final regressions and assess fit. Post hoc power analyses will be conducted when exploring differences in outcomes based on demographics (e.g., gender).

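### Aim 3 is worded as a feasibility question, but no planned analysis reports how many patients gave usable actigraphy data; separately, the visit table's actigraphy row disagrees with the procedures text

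*Combined protocol and SAP*

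**What the plan says.** **Objective.** In Statistical Analysis, Aim 3 is to "Explore the feasibility of utilizing actigraphy devices to capture postoperative functional outcomes", with the window given as "during their hospitalization and up to 2-weeks postoperatively following orthopaedic trauma".

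**Analysis.** The same paragraph plans a separate GEE for each actigraphy measure over the two-week postoperative period. Its examples are that "activity will be measured as average step per day and sleep will be measured as average nightly sleep efficiency and duration". A second stage depends on the first: "In the event a significant change in any of the objective outcomes, a linear mixed-effect model will be constructed", to compare the arms. No other Aim 3 analysis is described.

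**Procedures.** The actigraphy item under Discharge data (Study Procedures/Assessments) says patients are given a wrist device to "wear during their hospitalization and throughout their recovery until their 2-week follow up appointment". It covers activity as well as sleep. The device is returned at that appointment or mailed back in a prepaid envelope. On data quality it says "Wear time validation will be accomplished using the Choi algorithm", but gives no minimum number of valid days.

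**Visit table.** The one actigraphy row in Visit Schedule and Assessments is "Inpatient Sleep Actigraphy". It is marked at Visit 1 only and does not mention activity.

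**The concern.** A feasibility aim is answered by figures such as how many patients accepted the device, wore it long enough and returned it. Aim 3 specifies none of these. It moves directly to modelling steps and sleep, which presupposes that the recordings exist. The trial could then report trends in function under a feasibility heading without saying what share of patients supplied the data. Wear at home and return of the device are where losses are most likely, and they are also what a later trial would need to know about.

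The visit table is a second and independent matter. Its row is narrower than the procedures text and Aim 3 in both period (inpatient only) and content (sleep only). Staff who use the table as their checklist would get a different instruction from the one in the text.

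**Working it through.** The documents give no rate, threshold or sample size for Aim 3, so there is no figure to reproduce. The check has three parts.

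**1. Does any planned output measure feasibility?**
- GEE of each measure over time: estimates change in recorded function. It does not give the share of patients with recordings.
- Mixed model by arm: estimates a difference in recorded function, and runs only if the first stage finds a significant change.
- Choi wear-time step: this is data processing. It could supply valid wear days, but no valid-day rule, summary or criterion is attached to it.
- Study design and methods says the pilot will inform retention and outcomes assessment, but names no device measure.

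None of these reports the usable fraction.

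**2. Do the three descriptions of collection agree?**

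| Source | Period | Content |
|---|---|---|
| Aim 3 | Hospitalisation and up to 2 weeks after surgery | Steps and sleep |
| Procedures (actigraphy item) | Hospitalisation to the 2-week appointment | Sleep and activity |
| Visit table | Visit 1 (inpatient) only | Sleep |

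The first two broadly agree and the table row differs. Visit 2 is 2 weeks ± 7 days, so wear that ends at the appointment can end anywhere from day 14 − 7 = 7 to day 14 + 7 = 21.

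**3. Could this trial estimate a feasibility proportion usefully?**

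Inputs: 200 patients, 100 of them randomised to the intervention (Study design and methods), hence 100 per arm. Assumptions: one device per patient and a usable proportion p of 50% to 90%, since the documents give neither. The 95% half-width is 1.96 × √(p(1 − p)/n).

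| p | n = 200 (overall) | n = 100 (per arm) |
|---|---|---|
| 0.5 | 1.96 × √(0.25/200) = 6.9 points | 1.96 × √(0.25/100) = 9.8 points |
| 0.7 | 1.96 × √(0.21/200) = 6.4 points | 1.96 × √(0.21/100) = 9.0 points |
| 0.9 | 1.96 × √(0.09/200) = 4.2 points | 1.96 × √(0.09/100) = 5.9 points |

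The overall proportion would be estimated well enough to inform a later trial. The per-arm figures are less precise.

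**The case against.** **The procedures text already covers collection.** It specifies wear up to the 2-week appointment, activity as well as sleep, and two return routes. The table's labels are also loose: the row for the inpatient NRS pain score is marked at all four visits, so the word inpatient does not reliably limit timing there, and a mark at Visit 1 could simply show when the device is issued. This stands, and the row is no evidence that post-discharge data will be lost. It does not remove the discrepancy. The row has no Visit 2 mark, whereas the other device measure (MEMS) is marked at the follow-up visits, and it omits activity although steps are an Aim 3 measure.

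**Poor data capture would show in the models anyway.** A reader might infer that the GEE results would look the same whether 95% or 40% of devices gave usable data. That is not so. With 200 patients, the number analysed would fall from 0.95 × 200 = 190 to 0.40 × 200 = 80, and standard errors would grow by about √(0.95/0.40) = 1.54 times. Partial wear can also enter a GEE, and no analysis set is stated. What remains is that no planned output reports the usable fraction, and a reader should not have to deduce it from the width of an interval.

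**The aim is exploratory, in a pilot, and wear and return could be tabulated later.** This is also true, and it limits the gap to a missing prespecified summary. But if the valid-day rule is chosen after the data are seen, the feasibility figure depends on that choice.

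**Conclusion.** The point holds in two separate parts. First, Aim 3 asks about feasibility and no planned analysis answers it. This follows from the text alone and needs no assumption. Second, the actigraphy row in the visit table disagrees with the procedures text and Aim 3, and must be reconciled with them. Neither part causes the other.

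Two stronger readings are not supported. One is that Aim 3 requires two weeks of recording after discharge; its window starts in hospital and runs to two weeks after surgery. The other is that the period at home will go unobserved. On an assumed stay of 3 to 5 days (the documents give none), inpatient-only recording would cover 3/14 = 21% to 5/14 = 36% of a 14-day window, but this happens only if staff follow the table and disregard the procedures text.

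Severity is minor. The pain and opioid aims are unaffected, and the missing figure can come from data the trial already plans to collect. The precision figures rest on the assumed usable proportion and on one device per patient.

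**What to change.** 1. **Add a feasibility outcome to Aim 3 and place it first.** Define it as the proportion of all randomised patients, overall and by arm, with a returned device and at least a prespecified number of Choi-valid wear days between hospitalisation and the 2-week visit, with a 95% CI. Count days over the whole window, so that a long inpatient stay is not scored as failure. Set a number that a patient seen early in the ± 7-day window can still reach. Also report device return, mean valid days, and inpatient and post-discharge wear separately. Keep the GEEs as secondary and describe them as conditional on usable wear. If the team does not want a feasibility result, the alternative is to reword Aim 3 as an exploratory analysis of function.

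2. **Reconcile the visit table with the procedures text.** The row would read as actigraphy (sleep and activity): issued at Visit 1, worn until the 2-week appointment, returned at Visit 2 or by prepaid mail. A fixed day-14 end of wear should be avoided, because it would conflict with the appointment-based endpoint and the Visit 2 window.

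The cost is one table row, one valid-day rule and one descriptive analysis, with no new data collection. The downside is that the feasibility figure may prove unfavourable.

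### Exploratory Aim 3 compares the arms on actigraphy only if a measure first changes significantly over time, so arm estimates can go unreported when the trend is flat or small

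*Combined protocol and SAP*

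**What the plan says.** Aim 3 in the Statistical Analysis section is a feasibility aim: "Explore the feasibility of utilizing actigraphy devices to capture postoperative functional outcomes among patients during their hospitalization" and up to two weeks after surgery. It has two stages.

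- Stage one: "Generalized estimating equations (GEE) will be used to explore changes in functional outcomes" over the two-week period. The text adds that "Separate GEE will be computed for each actigraphy related measure". Steps per day, sleep efficiency and sleep duration are given as examples. No model terms are listed, and the arms are not mentioned.
- Stage two: "In the event a significant change in any of the objective outcomes, a linear mixed-effect model will be constructed to ascertain any significant differences". The contrast at this stage is the randomised one, "between participants in the intervention and the control arms over the two-week postoperative period".

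The actigraphy description, under Discharge data in Study Procedures/Assessments, names more measures: for sleep, "such as total sleep time, sleep latency, fragmentation, wake after sleep onset, and sleep efficiency"; for activity, "including total activity time, steps, physical activity intensity, and total energy expenditure". That is five plus four. No other section plans an arm comparison of actigraphy without the condition. Aims 1 and 2 model arm differences with no such condition.

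**The concern.** Whether a measure changes over two weeks and whether the arms differ are separate questions. If the GEE is a pooled time trend, a constant arm difference contributes nothing to it, and arms moving in opposite directions cancel. The randomised comparison is then fitted or skipped according to a test that does not address it.

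Two further points are left open:

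- **Scope of the gate.** Separate GEEs suggest one gate per measure. The reference to any of the outcomes may instead let one changing measure open the comparison for all.
- **Set of measures.** Three are examples and about nine are described, so two analysts could follow the text and report different comparisons.

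What is at stake is the completeness of an exploratory aim. With a gate per measure, measures with little overall trend would usually have no arm estimate. With an any-measure gate, all estimates are lost only when nothing changes detectably, but the chance of that depends on how many measures are tested.

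**Working it through.** **The plan's own figure.** Aim 3 has none. The only design figure ("A sample of 200 provides 85% power" for a 0.5-point pain difference) comes without an SD, correlation or number of repeats, so it cannot be reproduced. It has no bearing here.

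**Inputs from the documents.** 200 patients, 100 per arm; two-week window; α = 0.05 (stated for the power calculation and assumed for the gate, whose level is not given).

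**Assumed inputs.** 14 daily values, total SD 1, exchangeable within-person correlation ρ = 0.5, no missing data, two-sided tests. With complete data, a GEE slope test amounts to a test of the mean per-person slope.

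**Gate.** With days centred, Sxx = 14 × (14² − 1)/12 = 227.5. The SE of the pooled slope is √[(1 − ρ)/(Sxx × 200)] = √[0.5/45,500] = 0.003315. A rise of r SD over the window (13 intervals) gives z = (r/13)/0.003315, and the gate opens with probability Φ(z − 1.96) + Φ(−z − 1.96).

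**Direct test of a constant 0.35 SD arm difference.** SE = √[2(ρ + (1 − ρ)/14)/100] = √[2 × 0.5357/100] = 0.1035. Then z = 0.35/0.1035 = 3.38 and power = Φ(1.42) = 92%.

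**Case 1: gate per measure, constant 0.35 SD difference** (simulated columns: 20,000 runs per case).

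| Common rise (SD) | z | Gate opens, formula | Gate opens, simulated | Direct power, simulated | Power through gate, simulated |
|---|---|---|---|---|---|
| 0 | 0 | 5.0% | 4.9% | 91.9% | 4.5% |
| 0.05 | 1.16 | 21.3% | 21.1% | 92.2% | 19.5% |
| 0.1 | 2.32 | 64.1% | 64.3% | 92.0% | 59.0% |
| 0.2 | 4.64 | 99.6% | 99.6% | 92.4% | 92.0% |

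Power through the gate is close to gate rate × direct power, for example 0.643 × 0.920 = 0.592 against 0.590 simulated.

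**Case 2: opposite trends of ±0.15 SD.** The pooled slope is zero, so the gate opens about 5% of the time. The SE of the slope difference is √[2 × 0.5/(227.5 × 100)] = 0.00663, so z = (0.30/13)/0.00663 = 3.48 and direct power is Φ(1.52) = 94%. Simulated: 93% direct, 4% through the gate.

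**Case 3: control flat, intervention rising.** The pooled rise is half the intervention rise.

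| Intervention rise (SD) | Direct | Through gate |
|---|---|---|
| 0.2 | 64% | 41% |
| 0.3 | 94% | 87% |
| 0.5 | 100% | 100% |

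**Sensitivity of case 1 at a 0.1 SD rise.**

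| Change | Direct | Through gate |
|---|---|---|
| ρ = 0.3 | 99% | 49% |
| ρ = 0.7 | 83% | 71% |
| 60 per arm with usable data | 74% | 33% |

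**Any-measure gate.** If all trends are flat and the measures independent, it opens with probability 1 − 0.95^k: 14% for k = 3, 23% for k = 5, 37% for k = 9. For three measures correlated 0.3 to 0.7 the figure is 14% down to 11%. If one of three rises by 0.2 SD, it opens 99.7% of the time.

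**The case against.** The strongest reply has five parts.

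1. **The pooled trend is inferred.** The plan gives no GEE terms. If the GEE carried an arm-by-time term, the gate would partly address the arm question. This stands as a caveat. It does not rescue the rule: the plan does not say so, and reporting arm estimates only after such a test was significant would itself be selective.
2. **The literal wording favours the looser gate.** Any outcome may open the comparison for all, and steps may well rise during recovery from surgery. Under that reading the loss is probably small. This stands, but the separate GEEs support the other reading and the text does not settle it.
3. **The worst scenarios are stylised.** A constant difference needs the arms to differ from the first day, and exactly opposite trends are contrived. An effect that builds in one arm loses less (case 3). This also stands. The thresholds depend on the model too: if patients' own slopes vary with an SD of 0.5 over the window, the gate rate at a 0.2 SD rise is 95%, not 99.6%.
4. **No bias is shown.** With equal arms and this model, the pooled slope is independent of the arm contrast, so the estimates that are reported are not distorted. Correct: the cost is missing estimates.
5. **The aim is minor and partly covered.** It concerns feasibility, and Aim 1 models PROMIS scores, which include sleep and physical function, by arm without a gate. True, but those are self-reports and do not replace the objective measures.

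The count of nine is also loose: the sleep list is introduced as examples, and metabolic equivalents are mentioned as well.

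These points limit the weight of the concern. None supplies a reason for the condition.

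**Conclusion.** The concern holds as a low-stakes improvement. The plan states a rule that can leave a randomised comparison unfitted for a reason unrelated to that comparison, assuming the GEE is a pooled time trend.

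With a gate per measure, the loss is near total when the trend is flat, partial for rises of 0.05 to 0.1 SD, and negligible from about 0.2 SD. With an any-measure gate, nothing material is lost once one measure clearly changes. The effect sizes, correlation, number of days and completeness behind these figures are assumptions.

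Only the exploratory actigraphy aim is affected. Study design and methods does, however, list effect sizes among the things this pilot should inform, and arm estimates with intervals serve that purpose even when they are null.

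**What to change.** Delete the condition. For steps per day, sleep efficiency and sleep duration, fit one repeated-measures model each with arm, day and arm-by-day terms, whatever the GEE shows. Report the arm differences with 95% confidence intervals, labelled exploratory. Keep the pooled GEE as a description of recovery over time and state its terms. Any measure beyond these three should be named in advance.

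If the condition is kept, state whether the GEE includes arm, whether the gate applies measure by measure or to all at once, at what significance level, and which measures count.

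The cost is one or two sentences in the Statistical Analysis section and a few model fits on data already being collected.

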#### **Study design and methods:**

The pilot trial will include 200 patients – 100 randomized into LCS intervention. Prior to randomization, all patients will be given a standardized, validated, comprehensive social determinants of health assessment.

Patients will be randomized to either:

(1) LCS intervention - With *Opioid Risk Education*, patients will receive opioid education after completing the validated Opioid Risk Tool (ORT), a detailed substance abuse survey and mental health screening, and Naloxone education. *Therapeutic Intervention* will include the Community Resiliency Model CRM), progressive muscle relaxation, sound therapy. *Clinical Pain Coordination* will include directed referrals for complex needs, including mental health and substance use

- disorders, as needed. In addition to above mentioned 3 intervention components, all patients in the LCS intervention arm will also receive the current standard-of-care.
- **(2) No LCS intervention -** Patients will receive the current standard-of-care for pain management in the aftermath of trauma, which includes: a standardized prescription protocol, hospital-system approved discharge instructions which provide written instruction on how to taper opioid use, links to written/online resources for opioid misuse, overdose prevention, and State-approved disposal options.

Patients will be monitored throughout the course of the 1-year study for outcomes. They will also have the same quantity and quality of interaction with their usual clinical providers (orthopaedic trauma surgeon, physician's assistant).

This pilot trial will provide information on the effectiveness of LCS for pain intervention, as well as on study design, retention, effect sizes, and outcomes assessment. Our long-term goals are to determine whether LCSs are beneficial for decreasing opioid risk and improving pain management, and if so identify (1) the key effectiveness factors to the LCS intervention, (2) whether the LCS intervention can decrease overdose-related deaths, and (3) how to scale this model nationally, similar to the Child Life Specialist model.

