#### **Statistical Analysis:**

**Aim 1:** Examine differences in post-surgical patient-reported pain related outcomes between those in the intervention compared to the control arm. A multivariable mixed effects logistic regression model will be constructed to test the hypothesis that participants in the intervention arm have lower average NRS pain scores and PROMIS scores postoperatively compared to participants in the control arm. A separate linear mixed effects model will be constructed for each outcome. This modeling approach will enable the team to examine the mean differences in each patient-reported pain related outcome while adjusting for covariates (e.g., mental health history, BMI, surgery type, etc.).  The mixed effects modeling will account for potential collinearity between participants seen by the same surgeon by fitting a random effect for both factors. Models will be constructed using a Least Absolute Shrinkage and Selection Operator (LASSO) method. 50,51 An extension of traditional ordinary least squares regression model building, LASSO is a machine learning method capable of balancing bias and variance to build the most predictive model with a large subset of covarying factors using a penalized approach. A LASSO approach enables the team to systematically evaluate the variance introduced into regression modeling by hundreds of potential confounders. This unique quantitative capability will allow the research team to exploit the hundreds of data points collected from the electronic health records and the patient-reported outcomes collected per participant. The inclusion of these longitudinal measures makes it feasible to reduce statistical variation in the mixed effects models over time and therefore isolate the effect of the intervention. The fit of the most appropriate and still parsimonious model produced by the LASSO will be assessed based on the AIC score.

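### LASSO picks covariates from hundreds and the model is refitted on the same 200 patients without saying how arm enters; if arm is in the selection step, the arm standard error is too small

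*Combined protocol and SAP*

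**What the plan says.** All of this is in the Statistical Analysis section of the combined protocol and SAP.

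- **Aim 1** builds its models by LASSO. The stated reason is that "A LASSO approach enables the team to systematically evaluate the variance introduced into regression modeling by hundreds of potential confounders".
- The model is then judged by AIC: "The fit of the most appropriate and still parsimonious model produced by the LASSO will be assessed based on the AIC score".
- **Aim 2** follows the same route: "a systematic machine learning guided model construction approach will be used to also test the working hypothesis".
- **The Power paragraph** assigns the software. The glmnet "package will be used to determine which variables should be included in the regression models using a LASSO approach", and lme4 computes the final regressions.
- **Sample size.** Study design and methods says: "The pilot trial will include 200 patients – 100 randomized into LCS intervention".

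The plan does not say:

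- whether arm is penalised in the LASSO, left unpenalised, or kept out of it;
- whether a row is a visit or a patient, and how any cross-validation folds are formed;
- how the penalty is chosen;
- how many candidates there are, or which.

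It mentions no sample split, selective inference or other allowance for selection, and gives no other arm-comparison model for Aims 1 and 2.

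**The concern.** Candidates may be as numerous as patients. A covariate chosen because it fits these patients' outcomes takes up some chance variation. The lme4 refit then treats the chosen set as fixed in advance, so it can understate the residual between-patient variance and the arm standard error.

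Whether this harms the arm test depends on what the selection step sees. Suppose there is no effect and all candidates are measured before randomisation. Arm is then a random label, independent of outcomes and covariates. If covariates are picked from outcomes and covariates alone, arm is still a random label once the set is known, and the test stays close to nominal. If arm is in the LASSO during selection, that protection is lost. Covariates are picked to explain what is left after arm has taken its share, so the residual shrinks while the chance difference between arms does not.

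At stake is the error rate of the arm comparisons in Aims 1 and 2. The stated alpha of 0.05 would not be controlled if the analyst put arm in the LASSO to be sure of estimating it, which is an ordinary thing to do.

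**Working it through.** **1. The plan's own figure.** The plan says "A sample of 200 provides 85% power" with alpha 0.05 "to detect a difference as small as 0.5 in the mean pain score between the intervention arm and the controls". With 100 per arm and a two-sided test, 85% power requires SE = 0.5 / (1.96 + 1.036) = 0.167. The SD of the patient mean is then 0.167 / √(2/100) = 1.18. Dividing by √((1 + (m − 1)ρ)/m), with m = 3-4 visits and ρ = 0.2-0.8, gives a single-visit SD of 1.27-1.87. The documents give no SD or correlation, so 85% can be neither confirmed nor refuted. The calculation also makes no allowance for a selection step.

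**2. Inputs to the simulations.**
- From the documents: 200 patients, 100 per arm; 3 postoperative visits, or 4 with the inpatient visit; alpha 0.05.
- Assumed: 100, 200 or 300 candidates; within-patient correlation 0.3, 0.5 or 0.7; 0 or 10 true predictors, explaining 30% of between-patient variance when present; two-sided test. All candidates are patient-level and pre-randomisation; data are complete; there is no surgeon effect.

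**3. Method.** No arm effect was simulated. LASSO with 10-fold cross-validation chose the covariates, at either the minimum-error penalty or the one-standard-error penalty. A random-intercept REML model was refitted on the same patients and arm was tested at |z| > 1.96. Most settings had 600-800 runs (Monte Carlo error about 1 point at 5% and 1.5 points at 20%).

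**4. Results.**

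| How arm is handled | Folds | False-positive rate | Mean SE / true SD |
|---|---|---|---|
| In the LASSO, unpenalised | by row | 9.9-30.1% | 0.55-0.85 |
| In the LASSO, unpenalised | by patient | 5.8-16.3% | 0.73-0.94 |
| In the LASSO, penalised, may be dropped | by row | 3.1-17.1% | not summarised |
| In the LASSO, penalised, may be dropped | by patient | 0-5.8% | not summarised |
| Left out, added at the refit (200 and 300 candidates, correlation 0.5) | either | 1.7-4.9% | 0.93-1.36 |
| Six pre-specified covariates, no LASSO | none | 3.9-4.6% | 1.02-1.03 |

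With arm penalised and row-wise folds, the rate among trials that kept arm was 7.7-42%.

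**5. Do the two right-hand columns agree?** If the SE is r times the true SD, the rejection rate is roughly 2Φ(−1.96r). For r = 0.55 this is 2Φ(−1.078) = 28%; for 0.85, 2Φ(−1.666) = 10%; for 0.73, 2Φ(−1.431) = 15%; for 0.94, 2Φ(−1.842) = 7%. These match the simulated ranges, so the small standard error accounts for the inflation.

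**6. Cross-checks.**
- The actual glmnet and lme4 packages, arm unpenalised and row-wise folds, with 200 and 300 candidates (about 250 runs each): 21-25%, SE ratio 0.57-0.67.
- A separate simulation (200 candidates, 3 visits, correlation 0.5, 822 runs): 19% with arm unpenalised and row-wise folds (SE ratio 0.68), 6.4% with patient folds, 4.0% with arm left out of selection, 4.7% with five pre-specified covariates.
- One row per patient, as for inpatient MME/day (200 candidates, arm unpenalised, 328 runs): 13% at the minimum-error penalty, 6% at the one-standard-error penalty, 5% with arm left out.

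**The case against.** The strongest reply is that the plan never says arm goes into the LASSO. If it is added only at the refit, there is no inflation, even with stacked visits and row-wise folds. This is correct. A reader might infer that the plan as written carries a false-positive rate of 10-30%. The documents do not support that, because the figure rests on arm handling, row layout, fold unit and penalty, none of which they state.

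A reader might also blame glmnet for having no patient random effect. The results do not bear this out as the main cause. Row-wise folds do no harm when arm is outside the selection, and patient folds still reach 16.3% when arm is inside.

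Nor does the repeated-visits argument cover every outcome. Inpatient Pain and Opioid utilization defines inpatient MME/day as one average per patient. Only the selection effect can act there.

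Finally, Aim 1 asks for a parsimonious model, while the highest rates come from models that keep a large number of covariates. With 200 candidates, correlation 0.5 and arm unpenalised in the LASSO, capping the model at 10 covariates gave about 9%; the same cap with arm outside gave about 5% (1,800 runs). Without a cap, mixed-model AIC kept about 107 covariates and gave about 24%. Parsimony reduces the problem but does not remove it, and the plan sets no limit.

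**Conclusion.** The concern holds in conditional form. The plan selects from hundreds of covariates, refits on the same patients, makes no correction, and leaves open the choice that decides validity. If arm is unpenalised in the LASSO while covariates are chosen, the standard error is about 15-45% too small with row-wise folds (ratio 0.55-0.85) and about 6-27% too small with patient folds (0.73-0.94). The false-positive rates are then about 10-30% and 6-16%. If selection never sees arm, the rate is at or below about 5%.

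These ranges rest on the assumed candidate count, correlation and predictor strength; no single rate can be derived from the documents. Use of covariates measured after randomisation is a separate matter and was not simulated.

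**What to change.** **Primary arm comparison.** For each Aim 1 and Aim 2 outcome, fit arm, visit (where the outcome is repeated) and one short pre-specified list of covariates that allocation cannot affect, all forced in. Mental health history, BMI, surgery type and prior opioid use are examples. Label the LASSO models exploratory.

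**Starting values.** Include a starting value of the outcome only where it is recorded before allocation. Study Procedures/Assessments places the questionnaire battery after allocation, whereas Study design and methods places the social determinants survey before randomisation. That timing must be reconciled before anything from the battery is used as a baseline covariate. Inpatient MME/day has no starting value.

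**If LASSO is kept for adjustment.** Select from pre-randomisation covariates only, without arm in the selection step, assign folds by patient, and add arm at the refit. Setting the arm penalty factor to 0 is not a safe substitute: it keeps arm in the selection, and still gave 5.8-16.3% with patient folds.

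**Cost.** A change of wording in the Statistical Analysis section, and a check on when each listed covariate is recorded. Some precision from useful covariates outside the list is given up.
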